Dropout could occur when patients are ventilated for less than 24 hours after inclusion because of unexpected death, transfer to another ICU, or withdrawal of informed consent. We expect a maximum of 5% of these cases. Note a maximum of 5% of subjects are anticipated for which not 80% of mechanical ventilation time could be recorded within the allocated randomized ventilation mode due to documented technical reason. The recorded data will be used (with 'percent spent' calculated per the recorded time) for the primary analysis of the co-primary endpoints. As a sensitivity analysis, these values will be treated as missing data.

If the ventilation mode is modified by the site personnel by oversight or lack of training (deviating from the allocated randomization arm) and the subject's medical condition did not require it, the ventilation mode should be set back to allocated randomization arm. A protocol deviation and the event will be recorded in the eCRF accordingly.

If the site's principal investigator determines that the study is no longer in the subject's best interest (including the randomized ventilation mode) the subject's ventilation and study data collection ends. The site needs to complete an AE and the End of Study eCRF.

A. Gas exchanges targets:

SpO₂ will be kept in the ranges:

- 94 - 98% for normal lung, mild and moderate ARDS, and brain injured subjects
- 90-96% for moderate ARDS
- 88 - 95% for severe ARDS
- 90 - 94% for COPD without chronic hypoxemia or hypercapnia
- 88 - 92% for chronic hypercapnic subjects or subjects on long term oxygen

PaCO₂ will be kept in the range:

- 35 - 40 mm Hg for brain injury
- 35 - 50 mm Hg for normal lung, mild and moderate ARDS, COPD subjects without chronic hypercapnia
- ≥ 50 mm Hg in severe ARDS, severe COPD, and subjects with chronic hypercapnia if pH > 7.25

B. Passive subjects:

i. Ventilator settings:

Tidal volume will be kept in the range:

- 6-10 mL/Kg IBW for normal lung subjects, brain injury, and COPD subjects
- 4-8 mL/Kg IBW for ARDS

ii. Lung protection monitoring:

Plateau pressure will be measured at least twice a day and kept below 30 cmH₂O. Driving pressure will be measured at least four times a day and kept below 15 cmH₂O in all subjects.

In ARDS subjects, Plateau pressure between 30 and 35 cmH₂O will be accepted if driving pressure remains below 15 cmH₂O.

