8.3.2 Ventilation protocol in non-automated ventilation group

In order to standardize the non-automated ventilation process, Investigators will aim to keep the control arm (conventional non-automated ventilator) as close to the standard of care of the participating sites as possible.

General approach: The overall goals for the control arm ventilation protocol will be similar to those in the INTELLIVENT-ASV group including all recommendation available regarding gas exchanges targets, ventilator settings, protective ventilation targets, and weaning management (16, 32).

A. Passive subjects:

i. Ventilation mode

Any controlled mode will be possible such as volume control (CMV), pressure control (P-CMV), dual mode (APVcmv and APVsimmv), DuoPAP, SIMV, and P-SIMV. APRV will not be accepted. Tube resistance compensation (TRC) can be added.

ii. Ventilator settings

Respiratory rate will be adjusted according to PaCO_2 with a maximum of 35 Breaths/min.

Table 2: Management of pH and PaCO_2 :

$\text{pH} < 7.15$	$\text{pH}= 7.15 - 7.29$	$\text{pH}= 7.29 - 7.45$	$\text{pH} > 7.45$
Increase Respiratory rate up to 35 b/min and keep $\text{PaCO}_2 > 25$ mm Hg	Increase Respiratory rate up to 35 b/min and keep $\text{PaCO}_2 > 25$ mm Hg	Maintain VT around 6 mL/kg IBW in ARDS subjects and between 6 – 8 mL/Kg IBW for other subjects and maintain respiratory rate below 35 b/min.	Decrease respiratory rate but not below 6 /min
Consider NaHCO_3 If needed increase VT by 1 ml/Kg IBW or increase P_{INSP} by 2 cmH ₂ O with a maximum VT at 8 mL/Kg IBW for ARDS subjects and 10 mL/Kg IBW for other subjects. P_{PLAT} can be higher than 35 cmH ₂ O in case of extreme acidosis.	Consider NaHCO_3 If needed increase VT by 1 ml/Kg IBW or increase P_{INSP} by 2 cmH ₂ O with a maximum VT at 8 mL/Kg IBW for ARDS subjects and 10 mL/Kg IBW for other subjects. Keep $P_{\text{PLAT}} \leq 35$ cmH ₂ O.	Consider NaHCO_3 If needed increase VT by 1 ml/Kg IBW or increase P_{INSP} by 2 cmH ₂ O with a maximum VT at 8 mL/Kg IBW for ARDS subjects and 10 mL/Kg IBW for other subjects. Keep $P_{\text{PLAT}} \leq 35$ cmH ₂ O.	Consider NaHCO_3 If needed decrease VT by 1 ml/Kg IBW or decrease P_{INSP} by 2 cmH ₂ O with a minimum VT at 4 mL/Kg IBW for ARDS subjects and 5 mL/Kg IBW for other subjects.

PEEP will be set using PEEP/FiO₂ table, PEEP trial or transpulmonary pressure (based on the local hospital protocol).

PEEP will be kept in the range:

- 5-10 cmH₂O for normal lung subjects and COPD

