- 5-25 cmH₂O for ARDS subjects
- 5-15 cmH₂O for obese subjects

FiO₂ will be adjusted to the lowest to achieve SpO₂ target.

B. Spontaneous breathing subjects:

i. Ventilation mode:

Any assisted and spontaneous mode will be possible such as pressure support (SPONT), volume support (VS), SIMV, P-SIMV, and DuoPAP. APRV will not be accepted.

ii. Ventilator settings:

Ventilation support will be adjusted to keep tidal volume in the range:

- 6-10 mL/Kg IBW for normal lung subjects, brain injury, and COPD subjects
- 4-8 mL/Kg IBW for ARDS

Ventilation support will be adjusted to keep respiratory rate ≤ 35 Breaths/min.

PEEP will be kept in the range:

- 5-10 cmH₂O for normal lung subjects and COPD
- 5-15 cmH₂O for ARDS and obese subjects

C. Weaning

The INTELLiVENT-ASV or control arm ventilator protocols will be continued until subjects are able to breathe unassisted for 48 hours, death, ICU discharge, study withdrawal, the Principal investigator of the site determines that the study is no longer in the subject's best interest or day 28, whichever comes first.

i. Weaning trial

When the readiness to wean criteria will be fulfilled, a weaning trial will be performed on the same day for a duration of 30 min by any method with PEEP ≤ 5 cmH₂O and PS ≤ 7 cmH₂O: CPAP, tube compensation, minimal pressure support, T tube, or tracheostomy mask.

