8.3.3 Ventilation protocol in INTELLiVENT-ASV ventilation group

Subject allocated to INTELLiVENT-ASV group will be ventilated with this mode from inclusion to the end of the study. Tube resistance compensation (TRC) can be added.

A. Passive subjects:

i. Ventilator settings:

Clinician will set the IBW, subject condition, PetCO₂ and SpO₂ targets, PEEP ranges, and alarms and activate the controllers. The minimal FiO₂ will be set at 0.21. An arterial blood gas will be performed 30-60 min later in order to adjust the PetCO₂ target.

Table 3: Management of pH and PaCO₂:

pH < 7.15	pH= 7.15 – 7.29	pH= 7.29 – 7.45	pH > 7.45
Decrease PetCO ₂ targets by 5 mm Hg and keep PaCO ₂ > 25 mm Hg	Decrease PetCO ₂ targets by 5 mm Hg and keep PaCO ₂ > 25 mm Hg	No change	Increase PetCO ₂ targets by 5 mm Hg
Consider NaHCO ₃	Consider NaHCO ₃		

ii. Controller deactivation

PEEP and FiO₂ controller will be transiently deactivated if it is not possible to get a good SpO₂ signal with both finger and ear sensors. SpO₂ signal quality will then be re-assessed every 6h in order to restart oxygenation controller as soon as possible.

PEEP controller is by design deactivated when brain injury and chronic hypercapnia conditions are selected. PEEP will be set manually as in the non-automated ventilation group.

PEEP controller will not be deactivated in normal and ARDS conditions. Clinician can adjust PEEP ranges and use very narrow ranges if it is clinically needed.

Ventilation controller will be de-activated only if the clinical condition needs a %MV below 70% or above 200%.

Reasons and duration of controllers de-activation will be recorded in the eCRF.

B. Spontaneous breathing subjects:

i. Ventilator settings:

Clinician will set the IBW, subject condition, PetCO₂ and SpO₂ targets, PEEP ranges, and alarms and activate the controllers. The minimal FiO₂ will be set at 0.21. An arterial blood gas will be performed 30-60 min later in order to adjust the PetCO₂ target.

PEEP will be kept in the range:

- 5-10 cmH₂O for normal lung subjects and COPD
- 5-15 cmH₂O for ARDS and obese subjects

C. Weaning:

Weaning in the INTELLiVENT-ASV group will use quick wean function.

i. Quick wean activation

Quick wean will be activated when subject is stabilized with absence or minimum doses of sedation and vasopressor.

If subject has a coma Glasgow score above 8, quick wean function will be activated with SBT.

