10.4.5 Analysis of Primary Endpoints

The objective of this study is to compare the efficacy and the safety of the investigational automated ventilation (INTELLiVENT-ASV) with a control ventilation group (conventional non-automated ventilation) in ICU subjects.

The hypothesis is that INTELLiVENT-ASV is better than conventional non-automated ventilation in terms of efficacy and safety.

Efficacy and safety endpoints are composite endpoints and are based on six variables that will be continuously recorded during the study period:

- 1) Tidal volume (VT)
- 2) Maximum pressure (Pmax)
- 3) Oxygen saturation measured by pulse oximetry (SpO2)
- 4) End-tidal partial pressure of carbon dioxide (PetCO2)
- 5) Respiratory rate (RR) for spontaneous breathing subjects
- 6) Pmax-PEEP for passive ARDS subjects

Endpoints will be measured up to seven (7) days after randomization

Values for optimal, acceptable and sub-optimal ranges have been defined according to previously published studies (13, 14) and current recommendations. These ranges are adapted to the subject clinical condition and may be different for passive and spontaneous breathing ventilation periods.

Table 6: Values for optimal, acceptable and sub-optimal ranges

Variable	Ref.	Subject condition	Subject activity	Sub-optimal low	Acceptable low	Optimal	Acceptable high	Sub-optimal high
SpO2 (%)	20	None	Passive or active	< 90	≥90 and <94	≥94 and ≤98 Or > 98 if FiO2= 21%	> 98	NA
SpO2 (%)		ARDS	Passive or active	< 85	≥85 and <88	≥88 and ≤96 or > 96 if FiO2= 21%	>96	NA
SpO2 (%)	20	Brain injury	Passive or active	< 90	≥90 and <94	≥94 and ≤98 Or > 98 if FiO2= 21%	> 98	NA
SpO2 (%)	20	Chronic hypercapnia	Passive or active	< 85	≥85 and <88	≥88 and ≤92 or > 92 if FiO2= 21%	>92 and ≤98	> 98
PetCO2 (mm Hg)		None	Passive	< 25	≥ 25 and < 34	≥ 34 and ≤ 44	> 44 and ≤ 49	> 49
PetCO2 (mm Hg)	19	ARDS	Passive	< 25	≥ 25 and < 32	≥ 32 and ≤ 42	> 42 and ≤ 52	> 52
PetCO2 (mm Hg)		None or ARDS	Active	NA	< 25	≥ 25 and ≤ 45	> 45 and ≤ 55	> 55
PetCO2 (mm Hg)		Brain injury	Passive or active	< 29	≥ 29 and < 34	≥ 34 and ≤ 39	> 39 and ≤ 44	> 44
PetCO2 (mm Hg)		Chronic hypercapnia	Passive or active	< 25	≥ 25 and < 35	≥ 35 and ≤ 55	> 55 and ≤ 60	> 60
VT (mL/Kg IBW)	21	None	Passive	< 4	≥ 4 and < 5	≥ 5 and ≤ 8	> 8 and ≤ 10	> 10
VT (mL/Kg IBW)	15, 27, 35	ARDS	Passive	< 4	≥ 4 and < 5	≥ 4 and ≤ 8	> 8 and ≤ 10	> 10
VT (mL/Kg IBW)		None, ARDS, or brain injury	Active	< 4	≥ 4 and < 5	≥ 5 and ≤ 10	> 10 and ≤ 12	> 12

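### Protocol 8.3.1 A gives moderate ARDS two different SpO2 targets (94–98% and 90–96%), and nothing says which applies

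*Protocol*

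**What the plan says.** Section 8.3.1 of the protocol covers general management in both groups. Part A lists the SpO2 ranges in which subjects are to be kept. Three consecutive lines concern ARDS:

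- "94 - 98% for normal lung, mild and moderate ARDS, and brain injured subjects"
- "90-96% for moderate ARDS"
- "88 - 95% for severe ARDS"

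The PaCO2 list just below groups mild and moderate ARDS in the same way, "35 - 50 mm Hg for normal lung, mild and moderate ARDS, COPD subjects without chronic hypercapnia", but has no second line for moderate ARDS.

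Both arms then use the SpO2 target:

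- **Control arm (8.3.2).** The general approach shares the goals of the INTELLiVENT-ASV group, "including all recommendation available regarding gas exchanges targets". For passive subjects, "FiO₂ will be adjusted to the lowest to achieve SpO₂ target".
- **INTELLiVENT-ASV arm (8.3.3 A and B).** For passive and for spontaneously breathing subjects, "Clinician will set the IBW, subject condition, PetCO₂ and SpO₂ targets", along with other settings.

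Table 6 in section 10.4.5 scores the endpoints. It has a single SpO2 row for ARDS, not split by severity, with the optimal range given as "≥88 and ≤96 or > 96 if FiO2= 21" (per cent). The SAP refers back to that table and gives no SpO2 bands of its own.

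**The concern.** Both lines name moderate ARDS explicitly, so one cannot be read as a general rule and the other as its exception. A subject with moderate ARDS at 92% is below target on the first line and on target on the second. At 97% the reverse holds.

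The protocol leaves bedside staff in both arms to choose the band for these subjects. The choice affects the FiO2 they receive, and FiO2 and PaO2/FiO2 are secondary efficacy endpoints (5.2). Spontaneously breathing control subjects have even less guidance, because 8.3.2 B does not repeat the lowest-FiO2 rule and only the conflicting lines of 8.3.1 A remain.

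The protocol treats oxygen targeting as a safety matter. Section 3.4 says that both low and high oxygen can harm, and Annex A lists ventilation to a wrong target range among the anticipated serious device effects. Under 11.10, a deviation means not following the plan, and that cannot be decided here for readings on which the two lines disagree.

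**Working it through.** No sample size or error-rate figure is involved. The check compares intervals.

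**Inputs.** Line 1 = 94–98% and line 2 = 90–96% (8.3.1 A). Severe ARDS = 88–95% (8.3.1 A). Table 6, ARDS: optimal 88–96%, or above 96% if FiO2 is 21%; otherwise above 96% is acceptable high. Sub-optimal is below 85%, with no sub-optimal upper limit.

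**Overlap of the two lines.** From max(94, 90) to min(98, 96) = 94–96%, a width of 2 points. Together they span min(94, 90) to max(98, 96) = 90–98%, a width of 8 points. The floors differ by 94 − 90 = 4 points and the ceilings by 98 − 96 = 2 points.

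**Each zone against the two lines and Table 6:**

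| SpO2 in moderate ARDS | Line 1 (94–98%) | Line 2 (90–96%) | Table 6, ARDS |
|---|---|---|---|
| 90 to below 94% | below target | on target | optimal |
| 94 to 96% | on target | on target | optimal |
| above 96 to 98% | on target | above target | acceptable high (optimal if FiO2 = 21%) |

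**Effect on the co-primary endpoints.** All of line 2 lies inside the optimal range. Of line 1's 4-point width, 98 − 96 = 2 points lie above the optimal ceiling. Time spent there on FiO2 above 21% cannot count towards the primary efficacy percentage, and credit is actually lost only when the other applicable variables are optimal at that moment. No part of 90–98% is sub-optimal, so the choice of line does not by itself add time to the primary safety endpoint.

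**Which line fits the rest of the list.**

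| | Mild | Moderate | Severe |
|---|---|---|---|
| Moderate = 90–96%: floor / ceiling | 94 / 98 | 90 / 96 | 88 / 95 |
| Moderate = 94–98%: floor / ceiling | 94 / 98 | 94 / 98 | 88 / 95 |

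With 90–96% the bands step down with each grade of severity. With 94–98% moderate is identical to mild, and the floor then drops 94 − 88 = 6 points to severe. This pattern, and the matching grouping in the PaCO2 list, suggest that 'and moderate' was left in the first SpO2 line when a separate moderate line was added. That is an inference; the documents do not say so.

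**Search for a governing rule.** Sections 8.3.2 and 8.3.3 refer to the target without stating it by ARDS severity. Table 6 does not separate severities and defines scoring only. The SAP adds nothing. No precedence rule was found.

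**The case against.** The strongest reply accepts the conflict and disputes that it matters.

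- **A target of 94–96% meets both lines.** True, but it is a 2-point band that neither line states, and staff would have to work it out for themselves.
- **Passive control subjects are titrated to the lowest FiO2 that reaches target.** That pushes them towards the floor, 94% or 90%, and both are optimal in Table 6. This stands and limits the scoring effect in that group.
- **The mismatch with Table 6 is not peculiar to moderate ARDS.** Mild ARDS has an undisputed 94–98% target and is scored against the same 88–96% row. This also stands. Deleting two words leaves the mild ARDS mismatch in place, and lying inside the optimal range is only a supporting reason for choosing 90–96%.
- **Clinicians have other guidance.** Control care stays close to site standards, training covers ARDS, and an Investigator Brochure is referenced. Those materials are not available here, so the finding is about the protocol text and not about what staff do in practice.
- **The intended reading is apparent, and little else depends on it.** Randomization is not stratified by ARDS severity (6.2.1), and the modified ITT set depends on recording time, not on SpO2 targets. That supports a light correction. It does not make two conflicting instructions into one.

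**Conclusion.** The concern holds. The current protocol gives moderate ARDS two SpO2 targets in consecutive lines, they agree only at 94–96%, and neither document resolves them. The instruction applies to both arms.

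The consequence for the results is small. Primary-efficacy credit is at risk only above 96% and up to 98% on FiO2 above 21%. The primary safety endpoint is not directly affected, and no bias between arms is shown. The sample size, error rates and endpoint definitions are untouched. The total effect cannot be sized, because the documents do not give the number of moderate ARDS subjects or the time they spend in each zone.

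The conflict itself rests on no assumption. The view that 90–96% was intended is an inference from the severity gradient and the PaCO2 wording, and it needs the sponsor's confirmation.

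**What to change.** Delete 'and moderate' from the 94–98% SpO2 line in 8.3.1 A, so that moderate ARDS has only the 90–96% band. The sponsor should first confirm clinically that this is the intended target. If it is not, the 90–96% line should go instead, so that one target remains either way. Then notify sites in both regions.

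The cost is a two-word deletion that can go with the next protocol amendment, with the approvals that 11.9 requires before use, plus a site notice. Table 6, the SAP, the sample size and the analysis stay as they are. While the list is open, the sponsor may also wish to consider whether the mild ARDS target of up to 98% is meant to exceed the Table 6 ARDS optimal ceiling of 96%; this deletion does not settle that question.

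### In definable pH/PaCO2 windows the condition-specific PaCO2 targets of section 8.3.1 A and the pH-triggered rules of Tables 2 and 3 cannot both be followed, and the protocol does not say which prevails.

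*Protocol*

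**What the plan says.** Protocol section 8.3.1 covers management common to both arms. Part A is worded as a requirement ("PaCO₂ will be kept in the range") and sets three rows by condition:

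- "35 - 40 mm Hg for brain injury";
- "35 - 50 mm Hg for normal lung, mild and moderate ARDS, COPD subjects without chronic hypercapnia";
- at or above "50 mm Hg in severe ARDS, severe COPD, and subjects with chronic hypercapnia if pH > 7.25".

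Only the third row depends on pH.

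For passive subjects, each arm also has a table headed by pH. In Table 2 (section 8.3.2, control), both columns below pH 7.29 begin "Increase Respiratory rate up to 35 b/min and keep" PaCO2 above 25 mm Hg; the column above 7.45 begins "Decrease respiratory rate but not below 6 /min". In Table 3 (section 8.3.3, INTELLiVENT-ASV), both columns below 7.29 say "Decrease PetCO ₂ targets by 5 mm Hg and keep PaCO ₂ > 25 mm Hg"; the column above 7.45 raises the PetCO2 target by 5 mm Hg.

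The only entries in these tables that differ by condition are the tidal volume limits in Table 2. Section 8.3.2 mentions gas exchange targets among the goals of control ventilation and says respiratory rate follows PaCO2. Neither statement ranks section 8.3.1 A against Table 2, and nothing ranks it against Table 3.

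**The concern.** A clinician treating a passive subject has two instructions for the same quantity. One is keyed to the subject's condition, the other to pH. Where they disagree, two sites can each claim compliance while managing CO2 differently. The affected conditions are not marginal: ARDS, chronic hypercapnia and brain injury are three of the four randomisation strata.

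Two things are at stake. The first is subject safety, since in brain injury the two lower limits for PaCO2 are far apart. The second is consistency of delivery. PetCO2 is one of the six variables that score both co-primary endpoints, and in the INTELLiVENT-ASV arm the PetCO2 target adjusted under Table 3 is what the controller then pursues.

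**Working it through.** The plan gives no figure to reproduce here. The check sets the rules side by side and then asks whether the conflicting combinations can occur.

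**1. Direction of each rule**

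| Condition | State | Section 8.3.1 A | Tables 2 and 3 |
|---|---|---|---|
| Brain injury | pH < 7.29, PaCO2 at or near 35 | hold at 35 or above | lower; floor 25 |
| Brain injury | pH > 7.45, PaCO2 35–40 | hold at 40 or below | raise; no cap at 40 |
| Brain injury | pH > 7.45, PaCO2 > 40 | lower | raise |
| Severe ARDS, severe COPD, chronic hypercapnia | pH above 7.25 and below 7.29, PaCO2 about 50–55 | hold at 50 or above | lower; floor 25 |
| Same group | same pH band, PaCO2 < 50 | raise | lower |

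The third and fifth rows are strictly opposite. The others are hold against move. In the first row the lower limits differ by 35 − 25 = 10 mm Hg.

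**2. Step size in Table 3**

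The step is 5 mm Hg, which equals the width of the brain-injury range (40 − 35 = 5). Assume a stable gap between PaCO2 and PetCO2. One downward step from any PaCO2 below 40 then ends below 35, and one upward step from any PaCO2 above 35 ends above 40. In the third group, one downward step from 50 up to just under 55 ends below 50. Table 2 gives no step for respiratory rate, so in the control arm the conflict starts only when the limit is reached.

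**3. Can these states occur?**

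Henderson-Hasselbalch: HCO3 = s × PaCO2 × 10^(pH − 6.1), with s = 0.0307. The constants are assumptions, not from the documents.

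- Brain injury, pH 7.29: at PaCO2 35, 0.0307 × 35 × 10^1.19 = 16.6 mmol/L; at PaCO2 40, 19.0. The acidosis window needs bicarbonate below these values. Example: PaCO2 37 with bicarbonate 17 gives pH 7.28.
- Brain injury, pH 7.45, PaCO2 40: 0.0307 × 40 × 10^1.35 = 27.5. The strictly opposite cell needs bicarbonate above this. Example: PaCO2 43 with bicarbonate 30 gives pH 7.46.
- Third group: PaCO2 50 at pH 7.25 gives 21.7, and PaCO2 55 at pH 7.29 gives 26.2. Example: PaCO2 52 with bicarbonate 24 gives pH 7.28. For the strictly opposite cell, PaCO2 48 with bicarbonate 22 gives 6.1 + log10(22 / (0.0307 × 48)) = 7.27.

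With s = 0.03 the bounds become 16.3 and 18.6, 26.9, and 21.2 to 25.6. The picture is the same.

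**4. Illustration of size**

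Suppose bicarbonate is fixed and CO2 is lowered until pH reaches 7.29. Then the new PaCO2 = PaCO2 × 10^(pH − 7.29).

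- Brain injury from PaCO2 37.5: 34.2 from pH 7.25, 30.5 from pH 7.20, 27.2 from pH 7.15. All are below 35 and above 25.
- Third group: PaCO2 52 at pH 7.27 goes to 49.7; PaCO2 50 at pH 7.26 goes to 46.7.

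**5. Link to the endpoint**

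Table 6 scores PetCO2 in brain injury as optimal at 34–39 and sub-optimal below 29. If PetCO2 does not exceed PaCO2, a brain-injured subject at PaCO2 just above 25 and below 29, which the tables permit, is scored sub-optimal.

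**The case against.** The strongest reply is that section 8.3.1 A is the general section and can be read as bounding the arm-specific tables. A brain-injured subject held at 35 also satisfies a floor of 25. Section 8.3.1 A supplies the ceiling of 40 that the tables lack. A severe-ARDS subject at PaCO2 60 can be lowered and stay above 50. The surrounding text also ties the tables to PaCO2 and condition: section 8.3.2 mentions gas exchange targets, and in section 8.3.3 the clinician enters the subject's condition and PetCO2 target first. This stands in part. It removes the conflict in much of the overlap, but not at the range limits or in the strictly opposite cells, and the protocol does not state that reading.

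Both tables also suggest considering bicarbonate in the acidosis columns, another route to a higher pH. It is listed beside the order to lower CO2 and does not cancel it.

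For the third group, the figure of 50 could be meant as tolerance of higher values. The conflict would then be accept against correct. The wording is that of a range to be kept.

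The illustration is open to fair criticism. Neither table says to titrate to pH 7.29. The brain-injury examples imply bicarbonate of about 16, 14 and 13 mmol/L, a metabolic acidosis. The smallest breach, 49.7 against 50, is only 0.3 mm Hg.

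**Conclusion.** The contradiction is real but bounded. It arises in three windows: brain injury at or near PaCO2 35 with pH below 7.29; brain injury with pH above 7.45; and severe ARDS, severe COPD or chronic hypercapnia above pH 7.25 and below 7.29 with PaCO2 up to about 55. Orders are strictly opposite only in brain injury with PaCO2 above 40 and pH above 7.45, and in the third group with PaCO2 below 50.

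A reader might infer more, and the documents do not support it:

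- **Opposite orders for these conditions in general.** Outside the windows both rules can often be met, and most of the conflict inside them is hold against move.
- **Bias between arms.** The same ambiguity sits in both arms, randomisation is stratified by site and condition, and PetCO2 is scored against Table 6 rather than section 8.3.1 A. No direction of bias is shown.
- **The illustrated PaCO2 values as what the protocol would deliver.** They rest on fixed bicarbonate and titration to pH 7.29, neither of which the tables state.

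The documents give no basis for how often subjects enter these windows. What remains is a safety-relevant inconsistency and a source of site variation, which should be corrected.

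**What to change.** Reconcile section 8.3.1 A, Table 2 and Table 3 in one amendment. For each condition and pH band it should state which rule governs, with its target and its lower and upper PaCO2 limits. The same precedence and limits should apply in both arms. The wording cannot be identical, because the control arm acts through respiratory rate and tidal volume and the INTELLiVENT-ASV arm through the PetCO2 target. The amendment should also assign pH 7.29, which now falls in two adjacent columns of each table.

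Which values and which rule apply is for the sponsor's clinical leads; this review proposes none. The cost is a protocol clarification and a memo to sites, with no added data or subjects.
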